#### **9.2.5 Pregnancy**

If, following initiation of the study treatment, it is subsequently discovered that a participant is pregnant or may have been pregnant at the time of study exposure, including during at least 5 half-lives and 30 days after product administration, the investigator must immediately notify the BMS Medical Monitor/designee of this event and complete and forward a Pregnancy Surveillance Form to BMS Designee within 24 hours of awareness of the event and in accordance with SAE reporting procedures described in [Appendix 3](#).

In most cases, the study treatment will be permanently discontinued in an appropriate manner (eg, dose tapering if necessary for participant safety). Please call the BMS Medical Monitor within 24 hours of awareness of the pregnancy.

Protocol-required procedures for study discontinuation and follow-up must be performed on the participant.

Follow-up information regarding the course of the pregnancy, including perinatal and neonatal outcome and, where applicable, offspring information must be reported on the Pregnancy Surveillance Form.

Any pregnancy that occurs in a female partner of a male study participant should be reported to Sponsor or designee. In order for Sponsor or designee to collect any pregnancy surveillance information from the female partner, the female partner must sign an informed consent form for disclosure of this information. Information on this pregnancy will be collected on the Pregnancy Surveillance Form.

### **9.2.6 Laboratory Test Result Abnormalities**

The following laboratory test result abnormalities should be captured on the nonserious AE CRF page or SAE Report Form electronic, as appropriate. Paper forms are only intended as a back-up option when the electronic system is not functioning.

- Any laboratory test result that is clinically significant or meets the definition of an SAE
- Any laboratory test result abnormality that required the participant to have study treatment discontinued or interrupted
- Any laboratory test result abnormality that required the participant to receive specific corrective therapy

It is expected that wherever possible, the clinical rather than laboratory term would be used by the reporting investigator (eg, anemia versus low hemoglobin value).

### **9.2.7 Potential Drug Induced Liver Injury (DILI)**

Wherever possible, timely confirmation of initial liver-related laboratory abnormalities should occur prior to the reporting of a potential DILI event. All occurrences of potential DILIs, meeting the defined criteria, must be reported as SAEs (see [Section 9.2](#) and [Appendix 3](#) for reporting details).

Potential drug induced liver injury is defined as:

- 1) AT (ALT or AST) elevation > 3 times upper limit of normal (ULN)  
AND
- 2) Total bilirubin > 2 times ULN, without initial findings of cholestasis (elevated serum alkaline phosphatase)  
AND
- 3) No other immediately apparent possible causes of AT elevation and hyperbilirubinemia, including, but not limited to, viral hepatitis, pre-existing chronic or acute liver disease, or the administration of other drug(s) known to be hepatotoxic.

### **9.2.8 Other Safety Considerations**

Any significant worsening noted during interim or final physical examinations, electrocardiogram, x-ray filming, any other potential safety assessment required or not required by protocol should also be recorded as a nonserious or serious AE, as appropriate, and reported accordingly.

## **9.3 Overdose**

An overdose is defined as the accidental or intentional administration of any dose of a product that is considered both excessive and medically important. All occurrences of overdose must be reported as an SAE (see Section 9.2).

For this study, any dose of nivolumab greater than 10 mg/kg within a 24-hour time period will be considered an overdose. Also, any dose of BV exceeding 180 mg in a 24-hr period will be considered an overdose.

In the event of an overdose the [investigator/treating physician] should:

- 1) Contact the Medical Monitor immediately
- 2) Document the quantity of the excess dose as well as the duration of the overdosing in the CRF

Decisions regarding dose interruptions or modifications will be made by the investigator in consultation with the Medical Monitor based on the clinical evaluation of the participant.

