### **Nivolumab and Brentuximab vedotin arm**

Participants should receive nivolumab at a dose of 360 mg as a 30-minute infusion on Day 1 of each treatment cycle until progression, unacceptable toxicity, withdrawal of consent, or the study ends, whichever occurs first. No dose escalations or reductions of nivolumab are allowed. Premedications are not recommended for the first dose of nivolumab. For 30-minute infusions, infusion durations are  $\pm 5$  minutes. For Q3W dosing cycles, participants may be dosed within a  $\pm 3$  day window.

For participants in the nivolumab/BV arm, BV will be administered first as a 30-minute infusion followed by a minimum 30-minute rest prior to the nivolumab infusion. Brentuximab vedotin will be administered as a 1.8 mg/kg dose on Day 1 of each treatment cycle every 3 weeks for 16 cycles. In the absence of infusion-related reactions, the infusion rate for all participants should be calculated in order to achieve a 30-minute infusion period. Brentuximab vedotin must not be administered as an IV push or bolus nor mixed with other medications. Dosing of BV is based on participant's actual body weight. Doses must be adjusted for participants who experience a  $\geq 10\%$  change in weight from baseline. Other dose adjustments for changes in body weight are permitted per institutional standard. An exception to weight-based dosing is made for participants weighing greater than 100 kg; doses will be based on 100 kg for these individuals. Rounding is permissible within 5% of the nominal dose.

Nivolumab Injection, 100 mg/10 mL (10 mg/mL) is to be administered as an IV infusion through a 0.2-micron to 1.2-micron pore size, low-protein binding in-line filter at the protocol-specified doses. It is not to be administered as an IV push or bolus injection. Nivolumab injection can be infused undiluted (10 mg/mL) or diluted with 0.9% Sodium Chloride Injection, USP or 5% Dextrose Injection, USP to protein concentrations as low as 1 mg/mL. Instructions for dilution and infusion of nivolumab injection may be provided in the clinical protocol, pharmacy binder, or pharmacy reference sheet. Care must be taken to assure sterility of the prepared solution as the product does not contain any antimicrobial preservative or bacteriostatic agent.

Nivolumab infusions are compatible with polyvinyl chloride (PVC) or polyolefin containers and infusion sets, and glass bottles.

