### **Brentuximab Vedotin arm**

Brentuximab Vedotin will be administered as a 1.8 mg/kg dose on Day 1 of each treatment cycle every 3 weeks for 16 cycles as a 30-minute infusion. In the absence of infusion-related reactions, the infusion rate for all participants should be calculated in order to achieve a 30-minute infusion period. Brentuximab vedotin must not be administered as an IV push or bolus nor mixed with other medications. Dosing of BV is based on participant's actual body weight. Doses must be adjusted for participants who experience a  $\geq 10\%$  change in weight from baseline. Other dose adjustments for changes in body weight are permitted per institutional standard. An exception to weight-based dosing is made for participants weighing greater than 100 kg; doses will be based on 100 kg for these individuals. Rounding is permissible within 5% of the nominal dose.

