### **7.4.2 Brentuximab vedotin**

The recommended dose modifications for BV treatment associated toxicity are provided in [Table 7.4.2-1](#). Doses reduced for BV-related toxicity should not be re-escalated without discussion with the sponsor. Dose escalation of BV beyond 1.8 mg/kg is not permitted. Dose reductions below 1.2 mg/kg are not allowed.

If BV treatment is delayed for any reason, other treatments must be continued. Participants who require delay of BV should be re-evaluated frequently and BV dosing resumed when re-treatment criteria are met. Dose delays of more than 3 weeks may be allowed after discussion with the study medical monitor.

Recommendations for management of infusion related reactions due to BV are described in [Section 7.1.5](#).

Participants who discontinue nivolumab treatment due to a treatment-related AE may continue treatment with BV for a maximum of 16 cycles, or until disease progression or unacceptable toxicity, whichever occurs first. Participants who discontinue BV due to a treatment-related AE may continue to receive nivolumab treatment until disease progression or unacceptable toxicity.

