Suspected transmission of an infectious agent (eg, pathogenic or nonpathogenic) via the study treatment is an SAE.

Although pregnancy, overdose, cancer, and potential drug induced liver injury (DILI) are not always serious by regulatory definition, these events must be handled as SAEs. (See [Section 9.2.5](#) for reporting pregnancies).

Any component of a study endpoint that is considered related to study therapy should be reported as SAE (eg, death is an endpoint, if death occurred due to anaphylaxis, anaphylaxis must be reported).

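### A brentuximab vedotin dose that the 5% rounding rule permits (above 180 mg, up to 189 mg) is also a mandatory SAE under the flat 180 mg overdose trigger

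*Protocol*

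**What the plan says.** Four parts of the protocol bear on this.

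- **Dosing (7.1, both arms).** For the combination arm, "Brentuximab vedotin will be administered as a 1.8 mg/kg dose on Day 1 of each treatment cycle every 3 weeks for 16 cycles". The BV arm has the same dose and schedule. The dose follows actual body weight, and anyone heavier than 100 kg is dosed as if weighing 100 kg. Both arms add: "Rounding is permissible within 5% of the nominal dose". That sentence makes no exception at the cap and does not restrict rounding to downward.
- **Dose modification (7.4.2).** In a paragraph on changing the dose for toxicity: "Dose escalation of BV beyond 1.8 mg/kg is not permitted".
- **Overdose (9.3).** The section opens with a general definition, "any dose of a product that is considered both excessive and medically important", and then says "All occurrences of overdose must be reported as an SAE". It goes on to numeric rules for this study: more than 10 mg/kg in 24 hours for nivolumab, and for BV, "any dose of BV exceeding 180 mg in a 24-hr period will be considered an overdose".
- **SAE handling (Appendix 3).** Overdose is listed among events that are not always serious by regulatory definition, with the instruction that "these events must be handled as SAEs".

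**The concern.** The BV trigger sits exactly at the highest nominal dose and leaves no room for the rounding that 7.1 allows. A site could follow the dosing section and, with the same infusion, meet a categorical definition of overdose that carries a 24-hour SAE report. Two sites could classify the same dose differently, depending on which section they read.

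The trigger is also one fixed amount in milligrams, while the drug it covers is dosed by weight. How far a dose must exceed the prescribed amount before the numeric rule applies therefore depends on the participant's weight.

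What is at stake is consistent SAE classification in a safety description of 23 randomized participants. Sample size, power, alpha and the efficacy endpoints are not affected.

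**Working it through.** **Inputs.** From 7.1: 1.8 mg/kg, weight capped at 100 kg, rounding within 5%. From 9.3: the trigger fires strictly above 180 mg. From 7.4.2 and Table 7.4.2-1: escalation limit 1.8 mg/kg, reduced level 1.2 mg/kg. From Table 7-1: 50 mg vials. The protocol gives no participant weights and its eligibility criteria set no minimum weight, so the weights below are illustrations.

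**1. The plan's own figure.** Nominal dose = 1.8 × min(weight, 100). At the cap, 1.8 × 100 = 180 mg, which equals the trigger.

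**2. Highest permitted rounded dose.** 180 × 1.05 = 189 mg. The permitted range at the cap is 171 to 189 mg, and any dose in it above 180 mg meets the overdose rule.

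**3. Weight at which rounding can cross the trigger.** 180 / (1.8 × 1.05) = 95.24 kg. At 96 kg the permitted maximum is 172.8 × 1.05 = 181.4 mg. At 98 kg it is 176.4 × 1.05 = 185.2 mg.

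**4. Whether the escalation limit removes the conflict.** From 95.24 to 100 kg, the doses in question exceed 1.8 mg/kg of actual weight (up to 1.8 × 1.05 = 1.89 mg/kg). If 7.4.2 is read as limiting rounding too, they are not compliant and there is no conflict in that band. Above 100 kg the conflict remains under either reading if 7.4.2 is applied to actual weight. At 105 kg, 189 / 105 = 1.80 mg/kg; at 110 kg, 189 / 110 = 1.72 mg/kg. Such a dose satisfies both the rounding rule and 1.8 mg/kg, yet is an overdose under 9.3.

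**5. Whether ordinary rounding gets there.** The nominal dose never exceeds 180 mg, and 180 is a multiple of 1, 2, 5 and 10. Rounding to the nearest of any of these therefore never passes 180 mg. Rounding 180 mg up to whole 50 mg vials gives 200 mg; 200 / 180 = 1.11, which is outside the 5% allowance. Crossing the trigger compliantly needs a less usual upward adjustment, or a different vial size sourced locally (allowed by the Table 7-1 footnote, which names no size).

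**6. The flat trigger at lower weights.** A dose of exactly 180 mg does not exceed 180 mg, so it does not meet the numeric rule:

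| Weight | Nominal dose | 180 mg as mg/kg | Multiple of nominal |
|---|---|---|---|
| 50 kg | 90 mg | 3.60 | 2.00 |
| 60 kg | 108 mg | 3.00 | 1.67 |
| 70 kg | 126 mg | 2.57 | 1.43 |

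For an exactly doubled dose, 50 kg is the boundary: at 55 kg a doubled dose is 198 mg and does trigger. For a 50 kg participant reduced to 1.2 mg/kg (60 mg), 180 mg is three times the assigned dose.

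**The case against.** Several points on the other side are sound.

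**Low-weight doses can still be reported.** The numeric BV rule is an addition to the general definition in 9.3; it does not say that smaller doses cannot be overdoses. An investigator may judge a doubled dose at 50 kg to be excessive and medically important, and must then report it. A reader might infer that such doses fall outside 9.3 altogether and that the plan has a patient-safety gap. The text does not support that. What stands is narrower: below 180 mg, reporting rests on judgement alone.

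**Dosing errors are not lost from the record.** SAP section 7.4.1 plans BV dose in mg/kg, relative dose intensity with a category of at least 110%, and a by-participant dosing listing. The listing would show a doubled dose. The category would show it only in a short course: one doubled dose among n on-time doses gives (n + 1)/n, which is 17/16 = 106% for 16 doses and reaches 110% only for n of 10 or fewer. Harm from excess dosing is also collected as adverse events in its own right.

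**An overdose trigger need not mark compliance.** Nivolumab is a flat 360 mg, but its trigger is 10 mg/kg: 500 mg at 50 kg (500/360 = 1.4 times) and 1000 mg at 100 kg (1000/360 = 2.8 times). A dose can breach the protocol without being a reportable overdose. This answers any demand that the trigger track the prescribed dose exactly. It does not answer the reverse case, where a dose that breaches nothing is a mandatory SAE.

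**Section 7.4.2 should not be over-read.** A reader might take it to forbid any dose above 1.8 mg/kg. It forbids escalation, within a paragraph on toxicity-related changes, and does not mention rounding. Its bearing on the 95.2 to 100 kg band is therefore open.

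**Conclusion.** Wrong as written, minor. The conflict between 7.1 and 9.3 follows from the protocol's own figures: doses above 180 mg and up to 189 mg are permitted by one section and are mandatory SAEs under the other. It is clear above 100 kg, and it extends down to 95.2 kg if the escalation limit does not govern rounding. The general definition in 9.3 does not rescue this end, because the BV sentence is categorical. The flat trigger at lower weights is secondary: an undefined relation between the numeric rule and weight-based dosing, not a contradiction.

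A reader might go on to infer that the trial's SAE counts are distorted. The documents do not show that. They give no weights, no doses rounded upward and no dosing errors for the 23 participants, and ordinary rounding does not cross 180 mg. Enrollment is closed and BV is limited to 16 cycles, so further exposure is bounded. The probable practical effect is small; the actual frequency is unknown.

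**What to change.** The sponsor should reconcile 9.3 with the rounding and cap rules in 7.1 (both arms) and with the escalation limit in 7.4.2, so that a dose the rounding rule permits is not at the same time a mandatory SAE. The same text should say whether the escalation limit restricts rounding, and how the numeric trigger relates to weight-based dosing and to the general definition. Which passage moves, and any threshold, is for the clinical team.

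The cost is an administrative letter of a sentence or two. If no participant is still receiving BV, checking the dosing records against both rules before the safety tables are run would serve the same purpose for the report.

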## 9.4 Safety

Planned time points for all safety assessments are listed in the Schedule of Activities.

All screening assessments should be performed as indicated in [Section 2](#) and within a maximum of 28 days prior to randomization.

Baseline disease assessments should be performed within 28 days prior to randomization.

### **At Screening:**

- Medical history will be obtained to capture relevant underlying conditions
- Physical examinations should include weight, height, ECOG Performance Status, BP), heart rate, and temperature
- Screening laboratory assessments will be conducted locally

### **During the Treatment Period:**

- Participants will perform assessments as outlined in Section 2 and detailed in the Notes column
- The start and stop time of the study therapy infusions and any interruptions or infusion rate reductions should be documented
- Physical examinations are to be performed as clinically indicated. If there are any new or worsening clinically significant changes since the last exam, report changes on the appropriate non-serious or serious adverse event page
- Participants will be evaluated for safety if they have received any study treatment. Laboratory testing will be performed locally
- Additional measures, including non-study required laboratory tests, should be performed as clinically indicated or to comply with local regulations
- Some of the assessments referred to in this section may not be captured as data in the eCRF. They are intended to be used for safety monitoring by the treating physician. Additional testing or assessments may be performed as clinically necessary or where required by institutional or local regulations

**At Follow-Up:**

- Toxicity assessments will be continuous during the first two safety follow-up visits.
- Laboratory toxicities (eg, suspected drug induced liver enzyme evaluations) will be monitored during the follow-up phase via on site/local labs until all study treatment related toxicities resolve, return to baseline, or are deemed irreversible

**9.4.1 Physical Examinations**

Refer to Schedule of Activities, [Section 2](#).

**9.4.2 Vital signs**

Refer to Schedule of Activities, Section 2.

**9.4.3 Electrocardiograms**

Refer to Schedule of Activities, Section 2.

**9.4.4 Clinical Safety Laboratory Assessments**

[figure not shown]
- Investigators must document their review of each laboratory safety report
- All protocol specified laboratory tests are to be completed within 3 calendar days prior to dosing, analyzed and reported by the local lab  
Additional measures, including non-study required laboratory tests, should be performed as clinically indicated or to comply with local regulations
- Results of safety laboratory collections (ie, Chemistry and Hematology) must be obtained and reviewed in advance of study treatment dosing
- Laboratory parameters assessed in this study are identified in [Table 9.4.4-1](#).

[figure not shown]
**Table 9.4.4-1: Clinical Safety Laboratory Assessments**

Hematology	
Hemoglobin	
Hematocrit	
Total leukocyte count, including differential	
Platelet count	
Serum Chemistry	
Aspartate aminotransferase (AST)	Sodium
Alanine aminotransferase (ALT)	Potassium
Total bilirubin (TBili)	Chloride
Direct bilirubin	Calcium
Alkaline phosphatase	Phosphorus
Lactate dehydrogenase (LDH)	Magnesium
Serum Creatinine	Amylase
Blood Urea Nitrogen (BUN) or serum urea level	C-reactive protein
Albumin	
Uric acid	
Fasting glucose	
Creatinine clearance	
Thyroid Function Testing	
TSH	
Free T4	
Free T3	
Urinalysis	
Total Protein	
Glucose	
Blood	
Leukocyte esterase	
Specific gravity	
pH	
Serology	
Hep B/C (HBV sAG, HCV antibody or HCV RNA)	
Other Analyses	
Pregnancy test (WOCBP only: screening, predose, discharge)	

#### **9.4.5 Imaging Safety Assessment**

Any incidental findings of potential clinical relevance that are not directly associated with the objectives of the protocol should be evaluated and handled by the Study Investigator as per standard medical/clinical judgment.

[figure not shown]

[figure not shown]
## **10 STATISTICAL CONSIDERATIONS**

As of 17-Oct-2019, enrollment in this study was stopped at the decision of the Sponsor. At the time enrollment was stopped, 23 participants had been randomized. No formal statistical testing or inferential analyses will be performed. The statistical analyses as previously planned will only be conducted if appropriate in the final analysis. Further details are presented in the SAP.

### **10.1 Sample Size Determination**

The planned sample size for this study was to be approximately 340 randomized participants. The sample size of the study accounts for the primary efficacy endpoint, PFS. PFS will be evaluated for treatment effect at the overall alpha level of 0.05 (two-sided), with 90% power. As of 17 October 2019, enrollment was stopped. A total of 23 participants were randomized.

**Table 10.1-1: Schedule of Statistical Analyses**

	Interim Analysis	Final Analysis
Conditions	At least 131 PFS events and 6 months follow-up	At least 187 events
Expected timing	40 months (34 months + 6 months of follow-up)	45 months (34 months+ 11 months of follow-up)
Alpha level	Interim PFS analysis projected at 0.0148 level a	Final PFS analysis projected at 0.0455 level

a Using O’Brien and Fleming alpha spending function in case exact 131 PFS events are observed at the interim PFS analysis.

## 10.2 Populations for Analyses

For purposes of analysis, the following populations are defined:

Population	Description
Enrolled	All participants who sign informed consent
Randomized	Participants who had no post-randomization efficacy measure for the parameter being analyzed will be excluded.
Safety	All treated participants who received at least 1 dose of study treatment. Participants will be included in the treatment group that they actually received

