**Table 2-2: Procedural Outline During the Treatment Period (CA209812)**

Procedure	Cycle 1 Day 1 - Disease Progression or Unacceptable Toxicity	Notes  All windows proposed are calendar days. Procedures must be done within 72h prior to dosing unless otherwise specified. Dosing is to be performed every 3 weeks
Safety Assessments		
Targeted Physical Examination	X	Lymph node areas (for example, but not limited to, submandibular, cervical, supraclavicular, axillary, or inguinal lymph node), and abdominal organs (eg, spleen, liver)
Vital Signs	X	Includes body temperature, respiratory rate (RR), and seated blood pressure (BP) and heart rate.
Physical Measurements	X	Within 72 hours prior to dosing. Includes Weight and ECOG performance status ( Appendix 7 )
Adverse Events Assessment	Continuously	See Appendix 2/Section 9.2 . Assessed using NCI CTCAE v. 4.03.
Serious Adverse Events Assessment	Continuously	See Appendix 2/Section 9.2 . Assessed using NCI CTCAE v. 4.03
Review of Concomitant Medications	X	See section 7.7
Laboratory Tests	X	Within 72 hours prior to dosing to include CBC w/differential, AST, ALT, ALP, TBili, BUN or serum urea level, creatinine, Ca, Mg, Na, K, Cl, phosphate, LDH, glucose, amylase, lipase, c-reactive protein, albumin
Thyroid Function Testing	See note	TSH (reflex to free T3 and free T4 if abnormal result) to be performed every 9 weeks ( $\pm$ 7 days) from first dose regardless of dosing schedule.
Pregnancy Test for WOCBP	X See note	Serum or urine within 24 hours prior to first dose and then at least once every 4 weeks ( $\pm$ 7 days) regardless of dosing schedule.
Efficacy Assessments		
Radiographic Tumor Assessment FDG-PET-CT or PET-MRI scans from vertex to toes	See note	FDG PET-CT or PET-MRI will be performed at the end of cycle 5, 10, 15, and every 5 cycles until disease progression. FDG PET-CT or PET-MRI can be performed as clinically warranted for suspicion of recurrence during the non-protocol specified time points
B symptoms	See note	Collected Day 1 (prior to dosing) of every other cycle (cycle 1, 3, etc)

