## 10.3 Statistical Analyses

The SAP will be developed and finalized before database lock and will describe the selection of participants to be included in the analyses, and procedures for accounting for missing, unused, and spurious data. Below is a summary of planned statistical analyses of the primary and secondary endpoints.

[figure not shown]

[figure not shown]

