### 10.3.1 Efficacy Analyses

Endpoint	Statistical Analysis Methods
Primary	
The primary endpoint, PFS based on investigator assessment, will be compared in two randomized arms via a two-sided, log-rank test stratified by the same factors used in randomization. Participants who die without a reported progression will be considered to have progressed on the date of their death. Participants who did not progress or die will be censored on the date of their last tumor assessment. Participants who did not have any on study assessments and did not die will be censored on the randomization date. A participant who initiates a subsequent anti-cancer therapy will be censored on the date of last tumor assessment prior or on the start date of their subsequent anti-cancer therapy. Sensitivity analyses will be performed using different PFS definitions to assess the robustness of the primary analysis. The PFS curve, median and PFS rate at 6, 12, 18, and 24 months for each randomized arm will be estimated using the Kaplan-Meier product-limit method. Two sided, 95% confidence intervals for median PFS will be computed by Brookmeyer and Crowley method. A two-sided, 95% confidence interval for the PFS rates will be computed by Greenwood method. The hazard ratio (HR) and corresponding two-sided <math>100 * (1-\alpha)\%</math> (<math>\alpha</math> adjusted for the interim analysis) confidence interval will be estimated in a Cox proportional hazards model using randomized arm as a single covariate, stratified by the same factors used in randomization.

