4.2 Secondary Endpoints

4.2.1 BOR, CRR, ORR, PR, TTR, DOR and DOCR

Best Overall Response (BOR) of CR or PR or SD or PD will be evaluated for response evaluable participants according to the 2014 Lugano classification, based on BICR assessment.

The BOR is defined as the best response designation recorded between the date of randomization and the date of initial objectively documented progression per the 2014 Lugano classification or the date of subsequent therapy, whichever occurs first. For participants without documented progression or subsequent therapy, all available response designations will contribute to the BOR determination. For participants who continue treatment beyond progression, the BOR should be determined based on response designations recorded up to the time of the initial BICR defined progression.

Complete Response Rate (CRR): defined as proportion of participants who have achieved complete response (Lugano 2014 conference) as determined by the BICR prior to initiating any subsequent therapy among the randomized participants. For participants who continue treatment beyond progression, the complete response should be determined based on response designations recorded up to the time of the initial BICR defined progression.

ORR is defined as the number of participants with a Best Overall Response (BOR) of CR or PR, per the 2014 Lugano classification, based on BICR assessment, divided by the number of randomized participants

The objective response will be further characterized by the time to response (TTR). TTR is defined as the time from first dosing date to the date of the first response, based on BICR assessment. . TTR will be evaluated for responders only.

DOR is defined as the time from first response (CR or PR) to the date of initial objectively documented progression as determined using the 2014 Lugano classification or death due to any cause, whichever occurs first. For participants who neither progress nor die nor received

subsequent anti-cancer therapy, the DOR will be censored on the date of their last tumor assessment. Participants who start subsequent anti-cancer therapy without a prior reported progression will be censored at the last tumor assessment prior to or on the date of initiation of the subsequent anticancer therapy. The censoring scheme of DOR will be the same as the primary censoring scheme for PFS. This endpoint will only be evaluated in participants with objective response of CR or PR.

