6.3 Populations for Analyses

- **All enrolled participants:** All participants who signed an informed consent form and were registered into the IVRS. Analyses of the patients enrolled into the study but not randomized and the reason for not being randomized will be performed on the data set of all enrolled participants.
 - **All randomized participants:** All participants who were randomized to any treatment group in the study. This is the primary dataset for analyses of demography, protocol deviations, baseline characteristics, efficacy, [REDACTED].
 - **All treated participants:** All participants who received at least one dose of study medication. This is the primary dataset for dosing and safety.
 - **Response evaluable participants:** randomized participants whose change in the sum of diameters of target lesions was assessed (i.e.: target lesion measurements were made at baseline and at least one on-study tumor assessment).
- 

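### Protocol 10.2 describes the Randomized population only by an exclusion; this conflicts with the SAP's all-randomized denominator and, if followed, inflates CRR and ORR by N/(N-k)

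*Protocol*

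**What the plan says.** Protocol Section 10.2 lists three populations. The Enrolled and Safety rows say who belongs. The Randomized row says only who is removed: "Participants who had no post-randomization efficacy measure for the parameter being analyzed will be excluded".

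The SAP takes a different position:

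- Section 6.3 defines the randomized set as "All participants who were randomized to any treatment group in the study" and makes it the primary dataset for efficacy.
- Section 4.2.1 counts complete responses "as determined by the BICR prior to initiating any subsequent therapy among the randomized participants", and defines ORR as responders "divided by the number of randomized participants".
- Section 6.3 also keeps a separate response-evaluable set for participants with target-lesion measurements at baseline and at least once on study.

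The protocol's definitions of CRR and ORR in Table 4-1 and Section 10.3.1 name no other denominator. For progression-free survival (PFS), Section 10.3.1 keeps unassessed participants in the analysis: "Participants who did not have any on study assessments and did not die will be censored on the randomization date".

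Two statements limit the consequences. Protocol Section 10.3 says the SAP "will describe the selection of participants to be included in the analyses". Protocol Section 10, revised after enrollment stopped at 23 randomized participants, says "No formal statistical testing or inferential analyses will be performed".

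**The concern.** A population called Randomized should contain everyone randomized. This row drops participants according to something that happens, or fails to happen, after randomization, and does so separately for each parameter.

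The schedule makes unassessed participants plausible. Table 2-2 states "FDG PET-CT or PET-MRI will be performed at the end of cycle 5, 10, 15, and every 5 cycles until disease progression". With 21-day cycles, the first scheduled scan falls at day 105. Table 2-3 now says that participants who stop treatment before progression get no further PET imaging. Those without a response assessment would mainly be never-treated participants, early withdrawals, toxicity stops and deaths before the first scan. Early progressors would normally have a scan, since Table 2-2 allows unscheduled imaging on clinical suspicion.

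Under the SAP these participants are non-responders. Under the protocol row they disappear. In an open-label comparison of a combination with a single agent, nothing ensures that equal numbers disappear from each arm. At stake are the descriptive CRR and ORR with their exact intervals, which are main efficacy outputs now that testing has been dropped.

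**Working it through.** The plan gives no figure on this point to reproduce, so the check is the algebra plus examples under stated assumptions.

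**Inputs from the documents.** 23 randomized (Protocol 10.1); first scheduled scan at the end of cycle 5, which is 5 × 21 = 105 days (Table 2-2 and the cycle length in 5.1); exact Clopper-Pearson 95% intervals for response rates (Protocol 10.3.1).

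**Assumed.** Arms of 12 and 11, which sum to 23; the responder counts; and k. None of these is given.

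**Step 1: effect within an arm.** Let x be the responders among N randomized, of whom k have no response assessment. None of the k can be among the x, so the exclusion changes only the denominator:

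[x/(N-k)] ÷ [x/N] = N/(N-k)

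**Step 2: one arm, N = 12, x = 4.**

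| k | Multiplier | Rate | 95% CI |
|---|---|---|---|
| 0 | 1.000 | 4/12 = 33% | 10–65% |
| 1 | 12/11 = 1.091 | 4/11 = 36% | 11–69% |
| 2 | 12/10 = 1.200 | 4/10 = 40% | 12–74% |
| 3 | 12/9 = 1.333 | 4/9 = 44% | 14–79% |

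**Step 3: difference between arms.** Assume 7/12 and 4/11 complete responders, so the all-randomized difference is 58.3% − 36.4% = 22.0 points.

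| Unassessed | Difference | Shift (points) |
|---|---|---|
| 1 in each arm | 7/11 − 4/10 = 23.6 | +1.7 |
| 2 in the first arm only | 7/10 − 4/11 = 33.6 | +11.7 |
| 2 in the second arm only | 7/12 − 4/9 = 13.9 | −8.1 |

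The sign depends on where the unassessed participants fall, so no direction of bias can be claimed.

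**Step 4: PFS.** A participant censored at time zero is in no risk set at any event time. Removing that participant leaves the Kaplan-Meier curve, log-rank statistic and hazard ratio unchanged; only the reported N differs. This covers only participants censored at randomization. The row does not say whether a death with no prior scan counts as an efficacy measure for PFS. If it did not, a PFS event would be lost and the estimate would change.

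**Step 5: endpoints not affected.** Duration of response and duration of complete response are computed in responders only, so this row does not affect them.

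**The case against.** The strongest reply is that the plan already resolves this. Protocol 10.3 assigns the choice of participants to the SAP; the SAP is clear that efficacy uses all randomized participants; and Protocol 10.3.1 itself speaks of comparing the randomized arms. On that reading the inflation arises only if an analyst disregards the SAP. Moreover, k is unknown and may be zero, the larger shifts in the arm difference come from placing both unassessed participants in one arm, and with 23 participants, no testing and intervals as wide as 10–65%, no decision turns on one to three participants in a denominator.

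Much of this stands. It caps the importance of the point, and the examples show only what could happen. It does not remove the conflict. Section 10.3 delegates but does not withdraw the 10.2 row. The only SAP supplied is version 1.0 of 24-Feb-17, which is still built on blinded independent central review and predates Revised Protocol 01 of 08-Jan-2020. Whoever brings the SAP into line with the revised protocol will meet a protocol population that contradicts it. One could also say that the row's label names the base set; even so, the exclusion attached to that label is what conflicts with the SAP.

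**Conclusion.** The concern holds. The row is wrong as written, not merely short of detail: it contradicts SAP 6.3, the CRR and ORR denominators in SAP 4.2.1, and the protocol's own PFS rule. Followed literally, it multiplies CRR and ORR in each arm by exactly N/(N-k).

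The multiplier is certain; its realized size is not. Under the assumed arm of 12 it is 1.09 to 1.33 for k = 1 to 3, or about 3 to 11 points on a 33% rate, and it is 1 when k = 0. Any bias in the arm difference has no determined direction. For participants censored at randomization, PFS changes only in the reported N.

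This should be corrected before database lock, so that the denominator is not chosen after results are seen. With no formal testing planned, it does not threaten a confirmatory conclusion.

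**What to change.** Replace the Randomized row in Protocol 10.2 with: *All participants who were randomized, analysed by arm as randomized.* Add one sentence to 10.3.1: *Participants without a post-baseline response assessment count as non-responders for CRR and ORR and follow the stated censoring rule for PFS.* Label any evaluable-only summary as supportive.

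When the SAP is updated, carry the same rule over. Also align its Section 4.2.1, which evaluates best overall response in response-evaluable participants although ORR is built on best overall response with a randomized denominator.

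The drafting cost is one table row and one sentence, plus the ethics committee approval or notification that Appendix 2 of the protocol requires for a revision or an administrative letter. No procedure or data collection changes. Response rates may look slightly lower than under the exclusion.
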